#### **11.4.2.4 Psoriasis symptom inventory (PSI)**

Subjects will use an ePRO device to record their daily psoriasis symptoms using the PSI, a psoriasis specific patient reported outcome measure that has been developed on the basis of a literature review, in-depth physician interviews, psoriasis patient focus groups, and cognitive interviews ([Bushnell et al. 2013](#); [Appendix 5A](#)).

The PSI consists of eight psoriasis-specific questions. Subjects will be requested to rate the severity of their symptoms in the last 24 hours from ‘not at all’ to ‘very severe,’ ranging from 0 to 4. Total scores range from 0 to 32 with higher scores indicating worse symptoms.

The PSI takes about 3 minutes to complete.

Site staff will train the subject on the proper use of the ePRO device at the baseline visit. Subjects should be instructed to complete the PSI once per day. The ePRO must be completed in the evening within a specified time window (for the early termination visit only, the PSI may be completed earlier in the day).

The investigator should not question the subject’s answers. The investigator must review the data for timeliness and completeness.

Symptoms reported on the PSI will not be captured as AEs, unless they are specifically mentioned as an AE by the subject when they are asked the non-leading question: “How have you felt since I saw you last?” All data collected as part of the PSI will be reported in the trial report.

## **11.5 Safety assessments**

### **11.5.1 Vital signs**

Following vital signs must be measured:

- e) Blood pressure (BP), systolic and diastolic (mmHg)
- f) Heart rate (beats per minute)
- g) Temperature (Celsius with one decimal)
- h) Respiration rate (beats per minute)

The vital signs must be assessed after approximately 5 minutes in a resting position.

Clinically significant abnormal vital signs at the screening visit will be documented as medical history in the eCRF (see [Appendix 4D](#)). If an abnormal vital sign at any other visit than the screening visit is considered by the investigator to be clinically significant, it will be reported as an AE in accordance with the principles for data entry in Section [12.2](#).

### **11.5.2 Physical examination**

An abbreviated physical examination will be performed by the investigator and must include:

- i) General appearance
- j) Lymph nodes
- k) Dermatologic examination of the skin

Clinically significant abnormal findings at the screening visit will be documented as medical history in the eCRF (see [Appendix 4D](#)). If an abnormal finding at any other visit than the screening visit is considered by the investigator to be clinically significant, it will be reported as an AE in accordance with the principles for data entry in Section [12.2](#).

### **11.5.3 Weight**

The subjects must be wearing indoor clothing without shoes when weight is determined (kilograms, one decimal).

### **11.5.4 Pregnancy test**

Female subjects of childbearing potential must have a serum beta hCG performed at the trial site at the screening visit (visit 1). An urine pregnancy test must be performed at visits described in the schedule of trial procedures (see [Panel 2](#)). In case of a positive urine test, a serum beta hCG must be performed for the purpose of confirmation.

### **11.5.5 Adverse events**

AEs must be assessed and recorded as specified in Section [12](#).

## 11.6 Other safety assessments

### 11.6.1 Laboratory testing

#### 11.6.1.1 Safety laboratory blood analysis

Blood samples will be drawn for analysis of laboratory parameters according to the schedule of trial procedures ([Panel 2](#)).

The following blood sample tests will be analysed at central laboratory: serum chemistry, haematology, serum pregnancy, urinalysis (incl. urine pregnancy tests).

The central laboratory will provide a trial specific laboratory manual that outlines handling, labelling, and shipping procedures for all samples. All blood samples will be obtained by venepuncture before IMP administration. The date and time of sample collection will be recorded in the source documents at the site.

The serum chemistry, haematology and other tests are listed below:

#### Panel 10 Analysts

Chemistry	Haematology and differential	Other
Sodium Potassium Magnesium Bicarbonate Albumin BUN Creatinine Uric acid Total bilirubin Direct bilirubin Alk phosphatase AST ALT CRP	RBC Haemoglobin Haematocrit Platelets WBC Differential (absolute count and %):  - Neutrophils - Lymphocytes - Monocytes - Eosinophils - Basophils	Serum beta hCG QuantiFERON-TB Gold

The investigator must evaluate all results outside the reference range ('clinically significant' or 'not clinically significant') and sign and date. The signed and dated version of the lab results will be filed with the investigator's trial documentation. If a laboratory result is abnormal and of clinical significance, it will be up to the investigator's discretion to decide if the subject should be enrolled into the trial.

Clinically significant abnormal laboratory results at the screening visit will be documented as medical history in the eCRF (see [Appendix 4D](#)). If an abnormal laboratory results are found at any other visit than the screening visit is considered by the investigator to be clinically

significant, it will be reported as an AE in accordance with the principles for data entry in Section [12.2](#).

The laboratory provides results to the trial sites in SI units.

Handling, storage, destruction and shipment instructions are provided in a separate laboratory manual.

### 11.6.1.2 Estimate of total blood volume collected

Blood samples will be drawn for haematology, biochemistry and other tests. The blood volume at each visit depends on the visit and will vary from 6.0 mL to 12.0 mL. The total volume of blood drawn over the entire trial duration will be approximately 60 mL, which is less than the volume of blood drawn during a single blood donation (approximately 500 mL).

### 11.6.1.3 Safety urinalysis

Urine samples will be taken for analysis of the parameters listed below, at the visits specified in the schedule of trial procedures ([Panel 2](#)).

#### Panel 11 Urine analysis

**Urine:**

- Specific gravity
- pH
- Occult blood
- Protein
- Glucose
- Leucocyte esterase
- Ketones
- Urine pregnancy tests

## 12 Adverse events

- AEs and serious adverse events (SAEs) are defined in [Appendix 2: Definitions of adverse events and serious adverse events](#).
- Classification of AEs in terms of severity, causality and outcome are defined in [Appendix 3: Classification of adverse events](#).

### 12.1 Collection of adverse events

AEs must be collected from time of first trial related activity after the subject has signed the informed consent form until completion of the clinical trial. Hence, until the follow-up visit

scheduled at Week 32 for subjects allocated to brodalumab and at Week 26 for subjects allocated to fumaric acid esters.

AEs must be assessed by medically qualified personnel.

At all visits, the subject will be asked a non-leading question by the (sub)investigator about AEs, for example: “How have you felt since I saw you last?” No specific symptoms should be asked for.

## **12.2 Reporting of adverse events**

AEs reported by the subject or observed by the (sub)investigator must be recorded on the AE form of the eCRF and should be described in the following manner:

The *AE term* will be in precise English medical terminology (i.e. not necessarily the exact words used by the subject). Whenever possible, a specific diagnosis should be stated (for example allergic contact dermatitis).

The *duration* of the AE must be reported by the start date and stop date of the event. In addition, it must be recorded whether the AE started prior to start of IMP.

AEs must be classified in terms of severity, causality and outcome according to the definitions in [Appendix 3: Classification of adverse events](#).

### **12.2.1 Actions taken as a consequence of an AE**

*Action taken with trial treatment:* Any action taken with IMP as a consequence of the AE must be recorded (dose not changed, dose reduced, dose increased, drug interrupted, drug withdrawn, not applicable or unknown).

*Other action taken:* any other action taken as a result of the AE must be recorded (none, concomitant medication, concomitant procedure).

*Withdrawn due to AE:* it must be recorded whether the AE leads to withdrawal from the trial.

### **12.2.2 Reporting of serious adverse events**

The criteria that define an AE as serious (i.e. an SAE) are defined in Appendix 2: Definitions of Adverse Events and Serious Adverse Events

### 12.2.2.1 Investigator reporting responsibilities

Any SAE must be reported to LEO on the (paper) 'SAE Form – Clinical Trials' within 24 hours of first knowledge. This report should contain an assessment of available information on seriousness, severity, causal relationship to the IMP, comparator or trial procedure, the action taken, the outcome to date, and a narrative description of the course of the event.

The completed SAE form must be faxed or scanned and e-mailed to Global Pharmacovigilance LEO, using the following fax number or e-mail address:

- E-mail address: [[contact]](mailto:[contact])
- [contact]

It may be relevant for the (sub)investigator to enclose other information with the SAE form, such as anonymised reports of diagnostic procedures, hospital records, autopsy reports, etc.

Additionally, Global Pharmacovigilance LEO may request further information in order to fully assess the SAE. The (sub)investigator must forward such information to Global Pharmacovigilance, LEO upon request by fax or e-mail (see contact details above).

The investigator must notify the local independent ethics committee(s) (IEC(s)) of SAEs as required by current applicable legislation for the concerned country.

SAEs occurring after the completion of the clinical trial (i.e. after the safety follow-up visit defined in Section 11.1) should not be routinely sought or collected. However, such events must be reported, without undue delay, to Global Pharmacovigilance LEO (see contact details above) if the investigator becomes aware of them.

### 12.2.2.2 LEO reporting responsibilities

Global Pharmacovigilance, LEO is responsible for assessing whether or not an SAE is expected. The relevant reference documents for this clinical trial are:

- For brodalumab, the latest version of the company core safety information
- For fumaric acid esters, the latest version of the SmPC for Fumaderm®

The reference safety information for brodalumab ([Appendix 6](#)) is based on the company core data sheet (CCDS). The CCDS is chosen to ensure consistency in case evaluation and assessment of listedness/expectedness for different trials and spontaneous reporting. Further, changes to the safety profile are implemented in the CCDS immediately.

Global Pharmacovigilance, LEO will notify the regulatory authorities and concerned investigators of SAEs according to the current applicable legislation in Germany.

The IEC(s) will be notified of SAEs according to the current applicable legislation in Germany.

All SAEs which are assessed as causally related to the IMP(s) by either the investigator or LEO, as described in the ICH E2A guideline, and which are unexpected (suspected, unexpected serious adverse reactions (SUSARs)), are subject to expedited reporting to regulatory authorities, and IEC(s) according to the current applicable legislation in Germany. Investigators will be notified of these on an ongoing basis.

## **12.3 Other events that require expedited reporting to LEO**

### **12.3.1 Pregnancy**

Any pregnancy occurring during the clinical trial must be reported to LEO within 24 hours of first knowledge using the (paper) Pregnancy Follow-up Form (Part I). All such pregnancies must be followed up until delivery or termination and final outcome must be reported on the (paper) Pregnancy Follow-up Form (Part II) within 24 hours of first knowledge.

The completed Pregnancy Follow-up Forms must be faxed or scanned and e-mailed to Global Pharmacovigilance, LEO (see Section [12.2.2.1](#) for contact details).

Pregnant subjects must discontinue IMP.

### **12.3.2 Adverse events of special interest**

The following four adverse events of special interest (AESI) have been defined: SIB, serious infections, MACE defined as stroke, myocardial infarction, or cardiovascular death), and malignancy. These have been defined based on the known profile of brodalumab, emerging potential risks in the course of drug development, as well as other risks observed with other immune modulating biologics used for psoriasis.

The events might require that the investigator provides additional information to LEO (see [Panel 12](#)).

All AESI must be reported to LEO within 24 hours (see Section [12.2.2.1](#))

## Panel 12 Adverse events of special interest

Adverse event of special interest	Additional information to be provided
SIB	This AESI may be serious or non-serious. A specific adverse event form will need to be filled out whenever a SIB event is reported. This form will also include specific event related questions.
Serious infections	No additional information except for the described procedure for serious adverse event.
MACE	No additional information except for the described procedure for serious adverse event.
Malignancy diagnosed after randomisation (except basal cell carcinoma, squamous cell carcinoma, and cervical carcinoma in situ)	Procedure as described for serious adverse event including: Histology report Oncology assessment Treatment (surgery, radiation, chemotherapy, other)

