### Brodalumab safety:

During the brodalumab development programme, the most commonly reported adverse reactions in brodalumab-treated subjects included arthralgia, headache, fatigue, diarrhoea, and oropharyngeal pain (see reference safety information in [Appendix 6](#)). There were no very common adverse reactions.

During the brodalumab development programme, important identified and important potential risks have been identified to be further investigated after launch. These include serious infections, major adverse cardiovascular events (MACE), and malignancies. These important identified and important potential risks originate from the product's immunomodulatory activity and are shared by biologics in general. Furthermore, suicidal ideation and behaviour (SIB) have been identified as an important potential risks based on rare events occurring during the brodalumab development programme. A causal relationship between brodalumab treatment and SIB has not been established, and there is no known mechanism of action by which brodalumab would be associated with triggers of self-injurious or suicidal behaviour, such as depression, mood disorders, and affective disorders or behaviours ([Chiricozzi et al. 2016](#)).

During the 12-week placebo-controlled trial period in plaque psoriasis, infections were reported in 25.4% of patients treated with brodalumab compared with 23.4% of patients treated with placebo. The majority of infections consisted of nasopharyngitis, upper respiratory tract infection, pharyngitis, urinary tract infections, bronchitis, and influenza, which did not necessitate treatment discontinuation. Serious infections occurred in 0.5% of

patients treated with brodalumab and in 0.2% of patients treated with placebo. Higher rates of fungal infections, primarily non-serious skin and mucosal candida infections were observed in brodalumab patients compared to placebo patients, 1.8% versus 0.9%, respectively.

Antibodies to brodalumab developed in 2.7% (122/4461) of patients treated with brodalumab for up to 52 weeks in psoriasis clinical trials (0.3% of these patients had anti-brodalumab antibodies at baseline). Of these patients, none had neutralising antibodies.

No evidence of altered pharmacokinetic profile, clinical response, or safety profile was associated with anti-brodalumab antibody development.

For further details, please see the EU SmPC for Kyntheum®.

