12. Any positive finding in history of suicidal behaviour (e.g., ‘actual suicide attempts’, ‘interrupted attempts’, ‘aborted attempts’, or ‘preparatory actions’) based on the eC-SSRS questionnaire at screening or baseline.
13. Any positive finding in suicidal ideation of level 4 or 5 (‘some intent to act, no plan’ or ‘specific plan and intent’) based on the eC-SSRS questionnaire at screening or baseline.
14. A PHQ-8 score of  $\geq 10$  corresponding to moderate to severe depression at screening or baseline.
15. History of cancer:
  - a. Subjects who have had basal cell carcinoma, localised squamous cell carcinoma of the skin or in situ carcinoma of the cervix are eligible provided that the subject is in remission and curative therapy was completed at least 12 months prior to the date informed consent was obtained.
  - b. Subjects who have had other malignancies are eligible provided that the subject is in remission and curative therapy was completed at least 5 years prior to the date informed consent was obtained.
16. Known or suspected hypersensitivity to component(s) of the IMPs.
17. Current participation in any other interventional clinical trial, ending another interventional clinical trial less than 4 weeks prior to screening visit, or receiving other investigational agents (based on interview of the subject).
18. Subjects who have received treatment with any non-marketed drug substance (i.e. an agent which has not yet been made available for clinical use following registration) within the last 4 weeks prior to screening visit.
19. Previously enrolled in this clinical trial.
20. In the opinion of the (sub)investigator, the subject is unlikely to comply with the clinical trial protocol (e.g. due to alcoholism, drug addiction or psychotic state).
21. Subjects in close affiliation with the trial personnel (e.g. immediate family member or subordinate), subjects being a member of the clinical trial personnel, or being an employee of the sponsor or a CRO involved in the trial.

TRIAL ID: LP0160-1327	DATE: 17-APR-2018	VERSION: 4.0 PAGE 39 OF 108
-----------------------	-------------------	--------------------------------

22. Subjects under guardianship, hospitalised in a public or private institution, for a reason other than the research, or subject deprived of freedom.
23. Female subjects who are pregnant or breastfeeding.

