### 10.8.1 Reason for discontinuation of investigational medicinal product

Subjects must be **discontinued** from IMP in the event of:

- Anaphylactic reaction or other severe systemic reaction to IMP.
- An AE that, in the opinion of the investigator or sponsor's medical expert, contraindicates further dosing.
- Diagnosis of a malignancy during the trial, excluding carcinoma in situ of the cervix, or localised squamous or basal cell carcinoma of the skin.
- Evidence of pregnancy.
- Any infection that is opportunistic, such as active tuberculosis and other infections whose nature or course may suggest an immuno-compromised status.
- Severe laboratory abnormalities:
  - a) ALT and/or AST values  $>3 \times$  ULN with total bilirubin  $>2 \times$  ULN (unless elevated bilirubin is related to Gilbert-Meulengracht Syndrome).
  - b) Confirmed AST and/or ALT  $>5 \times$  ULN (for more than 2 weeks).
- If a subject is found to have any suicidal behaviour (actual suicide attempts, interrupted attempts, aborted attempts, or preparatory actions) or any suicidal ideation of level 4 (active suicidal ideation with some intent to act, without specific plan) or level 5 (active suicidal ideation with specific plan and intent) on any eC-SSRS assessment, the subject must be discontinued and referred to a mental health professional.
- If a subject is found to have a PHQ-8 score of  $\geq 15$ , corresponding to moderately severe to severe depression, the subject must be withdrawn and referred to a mental health professional.

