### 13.3.8.1 Adverse events

AEs will be coded during the trial according to the most recent version of Medical Dictionary for Regulatory Activities (MedDRA). All AEs will be presented by preferred terms (PT) and primary system organ class (SOC).

Treatment-emergent AEs (TEAEs) will be summarised, however, all AEs recorded during the course of the trial will be included in the subject data listings. An event will be considered treatment-emergent if started on or after the first day of IMP and no later than 5 half-lives after the last day on randomised treatment, or if started before the first use of IMP and worsened in severity thereafter. The tabulations described in the following will only include the treatment-emergent events.

An overall summary of the number of subjects with any TEAEs, the percentage of subjects with at least one event, the number of events and the event rate per 100 years will be presented. These summaries are done by SAEs, discontinuations from the trial due to AEs, treatment-related AEs, severe AEs, relation to device, outcome and AESIs.

Where there are several recordings of a specific AE within a subject, severity will be taken as the most severe recording for that specific AE. If a subject experience more than one AE of the same type, all severity evaluations should be recorded.

Where there are several recordings of causal relationship to a specific AE within a subject, causal relationship will be taken as the most-related recording from the last report of that AE.

Related AEs are defined as AEs for which the (sub)investigator has not described the causal relationship to IMP as 'not related'.

Summary tables based on SOC and PT are made for all TEAEs, serious TEAEs, related AEs, severe TEAEs, TEAEs reported as AESIs, AEs leading to withdrawal, and TEAEs with preferred term that are experienced by at least 5% of the subjects in any treatment arm or by at least 5% of all subjects.

Finally, relevant AE listings will be created.

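### Panel 12 exempts squamous cell carcinoma from the malignancy AESI without the limit to localised skin disease used in Sections 9.3 and 10.8.1, so a rare case could be classified inconsistently

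*Combined protocol and SAP*

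**What the plan says.** The protocol draws a boundary around malignancy in four places.

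- **Section 12.3.2, text.** Malignancy is one of four AESIs. The list closes with "cardiovascular death), and malignancy" and gives no exception. The section adds that "All AESI must be reported to LEO within 24 hours".
- **Panel 12.** The malignancy row reads "Malignancy diagnosed after randomisation (except basal cell carcinoma, squamous cell carcinoma, and cervical carcinoma in situ"). It asks for the SAE procedure plus a histology report, an oncology assessment and treatment details.
- **Section 10.8.1.** Study drug must be discontinued on "Diagnosis of a malignancy during the trial, excluding carcinoma in situ of the cervix, or localised squamous or basal cell carcinoma of the skin".
- **Section 9.3, criterion 15a (repeated in Appendix 1).** "Subjects who have had basal cell carcinoma, localised squamous cell carcinoma of the skin or in situ carcinoma of the cervix are eligible", subject to remission and a minimum time since curative therapy.

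Section 13.3.8.1 includes AESIs in the overall adverse event summary and plans a table by system organ class and preferred term for "TEAEs reported as AESIs". Section 6.2.1 explains the interest in this event. Of the brodalumab risks to be investigated further, it says: "These include serious infections, major adverse cardiovascular events (MACE), and malignancies".

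**The concern.** Sections 9.3 and 10.8.1 attach two limits to the squamous exception: the tumour must be localised, and it must be of the skin. Panel 12 carries neither, and no other part of the protocol supplies them for AESI reporting. A site that applies Panel 12 as written would not class an advanced or internal squamous cancer as a malignancy AESI. A site that works from the text of Section 12.3.2 would.

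Three things depend on that classification: 24-hour reporting as an AESI, the automatic request for histology, oncology and treatment information, and entry into the AESI summaries. The trial is open-label and investigators know the allocation, so a safety definition that leaves this to judgement is undesirable. When very few malignancies are expected, the classification of a single case also matters to how the AESI table reads.

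**Working it through.** The plan states no figure on this point, so there is none to reproduce. The check has two parts.

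**1. Apply each definition to the same cases, taking the words literally.**

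| Case after randomisation | 10.8.1: discontinue drug? | Panel 12: malignancy AESI? | 12.3.2 text: AESI? |
|---|---|---|---|
| Localised squamous carcinoma of the skin | No (exempt) | No (exempt) | Yes |
| Metastatic squamous carcinoma of the skin | Yes | No (exempt) | Yes |
| Squamous carcinoma of an internal site, e.g. lung or oesophagus | Yes | No (exempt) | Yes |
| Invasive squamous carcinoma of the cervix | Yes | No if the squamous exception governs; yes if the in situ limit governs | Yes |
| Carcinoma in situ of the cervix | No (exempt) | No (exempt) | Unclear |

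Rows 2 to 4 are the gap. Row 4 shows that Panel 12 also pulls against itself: it limits its cervical exception to in situ disease, but the unlimited squamous exception would take in an invasive squamous tumour at the same site.

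There is a smaller mismatch of the same kind. Basal cell carcinoma has no qualifier in Panel 12 or in criterion 15a, but is tied to the skin in Section 10.8.1.

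**2. How many malignancies could be involved?**

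Inputs: 102 subjects per arm (protocol summary and Section 13.1); 24 weeks of treatment; follow-up to Week 32 for brodalumab and Week 26 for fumaric acid esters (Section 8.1). The malignancy rate is not in the documents. A range of 0.5 to 1 per 100 person-years, all types together, is assumed.

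- On treatment, no drop-out: 204 × 24/52 = 94.2 person-years.
- With follow-up, no drop-out: 102 × 32/52 + 102 × 26/52 = 62.8 + 51.0 = 113.8 person-years.
- Expected malignancies of any type: from 94.2 × 0.005 = 0.47 to 113.8 × 0.01 = 1.14, so about 0.5 to 1.1.

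Section 13.1 plans for 50% drop-out on fumaric acid esters and under 40% on brodalumab. As an extreme floor, suppose that drop-outs contributed no time at all. Treatment exposure would then be 102 × 24/52 × (0.60 + 0.50) = 47.1 × 1.10 = 51.8 person-years, with 0.26 to 0.52 cases expected. True exposure lies above that floor.

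These counts cover every malignancy. The gap concerns only squamous cancers that are internal or no longer localised. The documents give no share for that subset, so the expected number affected is an unknown fraction of the counts above.

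**The case against.** The strongest reply is that Panel 12 is shorthand. It lists the same three tumours as Sections 9.3 and 10.8.1, and limiting the cervical exception to in situ disease suggests that the authors did not mean to exempt invasive cancer. That may well have been the intent, but nothing in the protocol says so, and sites apply the words they are given. The reply does show that the likely result is inconsistent capture, not certain omission. The unqualified text of Section 12.3.2 points the same way.

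A reader might infer that such a cancer would be lost from the safety data. The documents do not support this. Section 12.2 requires every adverse event to be recorded. Under Appendix 2 an internal or metastatic squamous cancer would very probably be serious, although cancer is not itself a listed criterion. Section 12.2.2.1 then gives the same 24-hour clock, a narrative, and a duty to supply further information on request. Section 13.3.8.1 provides tables of serious and severe events and of events leading to withdrawal, and lists all adverse events. What is at risk is the AESI entry and the automatic, as opposed to on-request, documentation.

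A reader might also infer that Panel 12 contradicts the discontinuation rule. It does not: one governs safety documentation, the other governs study drug, and an investigator can follow both. Their scopes differ without explanation.

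Finally, it is tempting to read the expected count of about one case or fewer as the size of the gap. It is an upper figure for all malignancies at an assumed rate, not an estimate for the affected subset.

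**Conclusion.** The inconsistency is real and stands in the current text: the squamous exception is unlimited in Panel 12, limited to localised skin disease in Sections 9.3 and 10.8.1, and absent from the text of Section 12.3.2. On a literal reading, a non-localised or non-cutaneous squamous cancer could be left out of the AESI tables and would not automatically trigger the Panel 12 information. Sites could also differ in how they class it.

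The practical size is small. About 0.5 to 1.1 malignancies of any type are expected with no drop-out, and fewer with it; only an unknown fraction would fall in the gap. This rests on the assumed rate of 0.5 to 1 per 100 person-years and on sites reading Panel 12 literally. The co-primary analyses, sample size and type I error are unaffected. It is a drafting inconsistency in a safety definition, worth correcting because the correction is easy and because deciding the classification after a case has occurred is worse than settling it beforehand.

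**What to change.** Reconcile the malignancy wording across Section 9.3 (criterion 15a), Section 10.8.1, the text of Section 12.3.2 and Panel 12. The simplest route is to give the Panel 12 reporting exception the limit that the protocol already uses elsewhere, so that beside basal cell carcinoma of the skin it covers only "localised squamous cell carcinoma of the skin or in situ carcinoma of the cervix". The sponsor should also make clear whether the localised limit is meant to apply to basal cell carcinoma, and should add a pointer from the text of Section 12.3.2 to the Panel 12 exception so that the two agree.

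This changes a reporting definition only. The discontinuation rule stays as it is, and no view is taken here on its content. The cost is one line in the protocol and a matching instruction for the AE form. The planned AESI tables need no change.
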